9. RESEARCH METHODS

9.1 STUDY DESIGN

Study design

- Non-interventional new user cohort study based on existing data (Medical Data Vision (MDV) database) using propensity score matching

Treatments Considered:

- Dabigatran and warfarin

Strength of the study design

- Channelling bias as well as differences in baseline risk of outcome occurrence between treatment groups will be addressed by the use of propensity score (PS) matching

Outcomes

- Primary outcome: stroke and systemic embolism
- Secondary outcome: major bleeding defined by any bleeding event associated with hospitalization claims and/or transfusion claims

9.2 SETTING

MDV clinical database is used.

Definition

1. Index date: the date of first oral anticoagulant prescription, namely warfarin or dabigatran
2. Baseline period: 12 months prior to and including the index date
3. Drug exposure period: period of time from index date to the end of drug treatment determined by having continuous record of prescription with less than 14 days of gap in prescription (grace period) or by switching to another OAC (end of index treatment is then considered to occur the day before the prescription of the new OAC)
4. Follow-up period: the day after index date to the earliest of treatment discontinuation, day before switch, end of continuous enrolment in the database, end of study period or death.

Inclusion criteria

1. >18 year-old with confirmed diagnosis of non-valvular atrial fibrillation (NVAF, ICD 10 code I48)
2. New starters of dabigatran or warfarin

Proprietary confidential information © 2017 Boehringer Ingelheim International GmbH or one or more of its affiliated companies

3. No prescription of other OACs for 12 months prior to the index date, defined as the first prescription of OACs (the period is defined as baseline period)
4. Has an index date between 14th of March 2011 to 30 June 2016

Exclusion criteria

1. Having less than 12 months of enrolment prior to the index date
2. Dialysis or kidney transplant recipients in baseline period
3. Having atrial flutter, valvular AF, mechanical valve placement, rheumatic AF, mitral valve prolapse/regurge/stenosis in baseline period
4. Having record of deep vein thrombosis or pulmonary embolism <6 months before AF diagnosis in baseline period

The symptoms, diseases, or treatments in these criteria are defined by ICD-10 code, disease name, or medical care activity name (see Table 1).

Table 1

Definition of symptoms/diseases/treatment for inclusion/exclusion criteria

| Symptoms/diseases/treatment | Definition | | |
|-----------------------------|------------|----------------|--|
| | ICD10 code | Disease name | Medical care activity name |
| Dialysis | - | - | Including “dialysis” |
| Kidney transplant | T861, Z940 | - | - |
| Atrial flutter | - | Atrial flutter | - |
| Valvular AF | - | Valvular AF | - |
| Mechanical valve placement | T820 | - | Including “mechanical valve placement” |
| Rheumatic AF | I05-I09 | - | - |
| Mitral valve prolapse | I340 | - | - |
| Mitral valve regurge | I341 | - | - |
| Mitral valve stenosis | I050, I342 | - | - |
| Deep vein thrombosis | I802 | - | - |
| Pulmonary embolism | I269 | - | - |

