| Data sources: MDV clinical database. The database is health insurance claims database. As of end of February 2016, MDV provides commercial | | | |

| | | | |
|---|---|---|---|
| Name of company: Boehringer Ingelheim | | | |
| Name of finished medicinal product: Prazaxa | | | |
| Name of active ingredient: Dabigatran etexilate | | | |
| Protocol date: 6 Jul 2017 | Study number: 1160.0288 | Version/Revision: Version 1.0 | Version/Revision date: Not applicable |
| claims for in and out-patients consisting of medical records from more than 12.94 million patients from 230 large acute care DPC hospitals. . Observation period is planned from 14 March 2010 to 30 June 2016 considering the launch date of dabigatran. | | | |
| Study size: | The previous study 1160.279 was a feasibility study to look into the treatment pattern of OACs in Japan and internal validity of MDV database including availability of co-variates to conduct 1:1 PS matching. For warfarin and dabigatran comparison, the number of AF patients meeting inclusion and exclusion criteria after matching was 4,427 in each cohort. | | |
| Data analysis: | 
This study plans no formal hypothesis testing. The planned analyses are descriptive in nature and results are to be interpreted in an exploratory manner.
 
1:1 Propensity score matching (PSM) was conducted to address potential channelling bias. Outcomes will be assessed in the PSM sample.
 
Patient characteristics prior to and after propensity score matching will be described stratified by treatment group.
 
Patients will be followed up from treatment initiation (index date) to the day of treatment discontinuation (defined as a treatment gap longer than 14 days past the number of days of supply of the last prescription), the day before a switch to a different anticoagulant, the date of disenrollment in MDV, the end of the study period, the occurrence of the event of interest, or death of the patient, whichever occurs first (as-treated analysis).
 
Number of observed events, number of patient years, the corresponding incidence rates and their 95% confidence intervals (CIs) will be reported.
 
Dabigatran and warfarin outcomes will be compared by estimating the hazard ratios (HRs) for the outcomes and their CIs using Cox regression.
 
Kaplan-Meier curves for event-free survival will be estimated.
 | | |

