9.9 LIMITATIONS OF THE RESEARCH METHODS

- Unobservable factors or factors not captured in the database such as laboratory data not equally distributed in the treatment groups that may also influence the outcomes could lead to unobserved confounding.
- The anticipated sample size might be limited which might lead to imprecise results. Therefore the study can only be considered to be exploratory. Based on the expected small sample size there is also the risk of pure chance findings. No hypothesis testing is planned,
- All information of each patient is from consent giving DPC hospitals. If patients have visits to other non-DPC medical institutions, these data are not included in the MDV data.

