9.11 SUBJECTS

The source population is Japanese patients who have claims data in MDV commercial database. In order to have claims in the database, the patients must have received some medical intervention, out or in-patient hospital visit, or pharmacy prescription from the DPC hospitals in Japan. DPC hospitals are large hospitals, often associated with medical schools or government funding, providing both acute and chronic medical care in Japan. Compared to non-DPC hospitals, they tend to provide more specialized, intensive medical care in addition to outpatient primary care tending to chronic disease requiring non-urgent care. MDV database has contractual agreement to receive claims data from approximately 12% of all DPC hospitals in Japan, and the selection is based on the willingness on the side of DPC hospitals to receive either financial compensation or data services from MDV. The inclusion and exclusion criteria are intended to select those Japanese atrial fibrillation patients who have non-valvular etiology and have newly initiated oral anti-coagulants for stroke prevention. The data cut-off of 14 Mar 2011 to 30 June 2016 is to select those claims that have occurred after the launch of dabigatran and to the most recent available data cut from MDV at the time of protocol writing.

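### The 12-month enrolment rule does not secure new-user status in a database that sees only contributing-hospital contacts, and the plan never defines enrolment

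*Combined protocol and SAP*

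**What the plan says.** Two rules in section 9.2 carry new-user status. Exclusion 1 removes patients "Having less than 12 months of enrolment prior to the index date". Inclusion 3 asks for "No prescription of other OACs for 12 months prior to the index date"; the abstract extends this to any oral anticoagulant (OAC).

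Enrolment returns as a censoring event. Section 9.2 ends follow-up at the earliest of five events, the last three being "end of continuous enrolment in the database, end of study period or death". The abstract lists six, among them "the date of disenrollment in MDV", and adds the event of interest. Neither place says how enrolment or its end is found in the data.

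The data source is described differently elsewhere. Section 9.11 says: "In order to have claims in the database, the patients must have received some medical intervention, out or in-patient hospital visit, or pharmacy prescription", in each case from a DPC hospital, and puts MDV's coverage at about 12% of DPC hospitals. Section 9.9 concedes: "If patients have visits to other non-DPC medical institutions, these data are not included in the MDV data". Section 9.12 names two measures against bias: restriction to new users and propensity score matching.

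**The concern.** If a person appears in MDV only through contact with a contributing hospital, a 12-month window without an OAC prescription can mean two things: the patient took none, or the patient was not seen. The rule as written does not separate them. A patient already established on warfarin at a clinic can become a new starter at the first hospital prescription.

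Established users have already come through the early treatment period, so their event rate may differ from that of true starters. If they are unevenly spread between the arms, the hazard ratio is distorted. Matching cannot correct this directly. Prior use elsewhere is unobserved, and the histories and co-medications in section 9.3.3 come from the same incomplete records.

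The limitation in section 9.9 mentions only non-DPC institutions and is not linked to new-user status. With about 12% coverage, prescriptions at most other DPC hospitals are unseen too.

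**Working it through.** **Who passes the rules.** The plan gives no coding for enrolment. Suppose, as an assumption, that it begins at the first MDV record.

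| Patient | Section 9.2 as written | With the observed-contact rule proposed below |
|---|---|---|
| No MDV record before the index visit | Excluded | Excluded |
| One record more than 12 months before index, none in the baseline year, OAC from a clinic | Passes as new user | Excluded |
| Hospital visits in the baseline year for other reasons, OAC from a clinic | Passes as new user | Still passes if there is also a record at least 12 months before index |
| Seen in the baseline year and before it, no OAC anywhere | Passes correctly | Passes correctly |

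The second row is the defect that can be mended. The third row shows the limit of any rule based on MDV alone.

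**The plan's own figures.** Section 9.5 combines hazard ratios of 0.45 (21% of patients) and 0.81 (79%): exp(0.21 × ln 0.45 + 0.79 × ln 0.81) = 0.716, as stated.

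Table 9 is reproduced to within one percentage point by

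power = Φ( ln(1.378/HR) / √(4/D) − 1.96 ), with D = 4,421 × 0.40487 × rate × (1 + HR).

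The hazard-ratio column was not legible in the text reviewed, so 0.5 to 0.9 in steps of 0.1 is assumed. At 0.03 per year this gives 0.995, 0.971, 0.899, 0.762 and 0.576, against the printed 0.996, 0.974, 0.905, 0.770 and 0.583. At HR 0.716, D = 4,421 × 0.40487 × 0.03 × 1.716 = 92.1 events and power is 0.881. (That leaves an 11.9% chance of the upper bound passing 1.378, where section 9.5 says less than 10%. This is a separate matter and is not pursued here.)

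**Illustration of the possible effect.** The documents give no figure for prior OAC use outside MDV, so the following inputs are assumptions. Let a share q of the warfarin arm be established users with r times the new-user hazard, and let the dabigatran arm have none. Then

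observed HR = 0.716 / (1 − q(1 − r)),

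and power follows from the formula above with D = 4,421 × 0.40487 × 0.03 × (1 − q(1 − r) + 0.716).

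| Observed HR (power) | r = 0.5 | r = 0.7 | r = 0.9 |
|---|---|---|---|
| q = 10% | 0.754 (0.814) | 0.738 (0.844) | 0.723 (0.870) |
| q = 20% | 0.796 (0.725) | 0.762 (0.798) | 0.731 (0.857) |
| q = 30% | 0.842 (0.617) | 0.787 (0.745) | 0.738 (0.844) |

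**Sensitivity of the direction.** If established users arriving at hospital are at higher risk, say r = 1.2, the ratio moves the other way: 0.716/1.02 = 0.702 at q = 10% and 0.716/1.06 = 0.675 at q = 30%. If q and r are the same in both arms, the factor cancels and the ratio stays at 0.716.

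**The case against.** - **The criteria have already been applied.** The abstract reports 4,427 matched patients per cohort meeting the criteria in study 1160.279, so a working rule for enrolment evidently existed. This stands: the rule is unstated, not impossible to apply. Section 9.7.1 refers to that study's protocol only for matching detail, however, so the reader of this plan cannot tell whether the rule protects new-user status.

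- **Follow-up still closes.** A reader might infer that follow-up has no usable end. The documents do not support that. Disenrolment is one of five or six ends, and discontinuation, "defined as a treatment gap longer than 14 days past the number of days of supply of the last prescription", needs no enrolment file, nor do the switch and study-end rules. A reader might also suppose that follow-up is cut at the last MDV record, inflating the incidence rates. The plan nowhere says so, and no figure for such inflation can be drawn from it.

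- **The propensity score helps.** It includes year of initiation, time from AF diagnosis to OAC start and history of hospitalisation. Matching on year balances calendar time, which bears on the post-launch argument, but it does not detect warfarin taken elsewhere within a given year.

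- **The limitation is disclosed and the study is exploratory.** Both are true, and they temper the severity. Section 9.12 nonetheless relies on new-user restriction without noting that the data gap weakens it.

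**Conclusion.** The concern holds in this form: the 12-month rule, read with the plan's own description of MDV, can admit established users as new users, and so does not secure one of the two bias controls in section 9.12. This rests on the text and needs no numerical assumption beyond a reading of enrolment that accepts an old contact.

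A reader might go further and conclude that the hazard ratio is biased against dabigatran. Established dabigatran users could hardly exist at the March 2011 launch, so an excess in the warfarin arm soon afterwards is plausible. But section 9.11 describes DPC hospitals as giving more specialised care, so patients arriving from clinics may be at higher risk, and established users of both drugs may occur later in the window. The range of 0.72–0.84 is illustrative and assumes established users in the warfarin arm only, with a lower hazard. The documents establish neither direction nor size.

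For censoring, the conclusion is narrower: one listed end of follow-up is undefined and should be replaced by a date that can be determined.

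**What to change.** 1. Restate exclusion 1 as observed contact: an MDV record at least 12 months before the index date, and at least one MDV record in the 12 months before it other than the index visit, none with an OAC.
2. Repeat the primary hazard ratio requiring a record in each half of the baseline year, and report both estimates.
3. In section 9.2 and the abstract, replace the enrolment-based censoring term with a last observable date that MDV can supply, for example the end of the hospital's data contribution. Keep the gap, switch, event, death and study-end rules. Simply deleting the term would count the remaining supply days of patients who can no longer be observed as event-free.
4. State in section 9.9 that OAC use outside contributing hospitals may misclassify new-user status.

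The cost is protocol text and a re-run of selection and matching on data already held. Some patients are lost. As an illustration, losing 10% widens the standard error by 1/√0.9 = 1.054, about 5%; the documents give no basis for the actual loss. Because section 9.4 starts the data on 14 March 2010, exactly 12 months before the first index date, the earliest starters would be hit hardest unless earlier records can be used. The cohort also shifts towards patients with regular hospital contact. OAC use elsewhere is reduced as a source of error but not eliminated.

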4. ABSTRACT

| | | | |
|---|-----------------------------------|---|---|
| Name of company: Boehringer Ingelheim | | | |
| Name of finished medicinal product: Prazaxa | | | |
| Name of active ingredient: Dabigatran etexilate | | | |
| Protocol date: 6 Jul 2017 | Study number: 1160.0288 | Version/Revision: Version 1.0 | Version/Revision date: Not applicable |
| Title of study: Comparative Effectiveness and Safety between Warfarin and Dabigatran Using Real World Claims data of Japanese Non-valvular Atrial Fibrillation Patients | | | |
| Rationale and background: Real-world data about the characteristics of patients with NVAF initiating an oral anticoagulant (OAC) in Japan has been scarce to date. The purpose of this study is to compare the effectiveness and safety of dabigatran and warfarin using the MDV database. | | | |
| Research question and objectives: To compare the effectiveness (stroke/SE) and safety (major bleeding) in patients with atrial fibrillation and newly treated with dabigatran and warfarin in the real world Japanese setting using a claims database | | | |
| Study design: A non-interventional study based on existing health insurance claims data | | | |
| Population: Medical Data Vision (MDV) clinical database is used. OAC-naïve, adult patients with NVAF initiating dabigatran or warfarin between 14 March 2011 (considering the launch date of dabigatran) and 30 June 2016 will be enrolled. Inclusion criteria: patients aged >18 year-old with confirmed diagnosis of NVAF (ICD 10 code I48), having a first prescription (index date) of either dabigatran or warfarin between 14 March 2011 to 30 June 2016, having no prescription of any OACs for 12 months prior to the index date (this period is defined as the baseline period). Exclusion criteria: patients having less than 12 months of enrolment prior to the index date, being dialysis or kidney transplant recipients in baseline period, having either atrial flutter, valvular AF, mechanical valve placement, rheumatic AF, and/or mitral valve prolapse/regurge/stenosis in baseline period, and having record of deep vein thrombosis or pulmonary embolism < 6 months before AF diagnosis in baseline period. | | | |
| Variables: Baseline characteristics of patients (age, sex, clinical history), year of initiating treatment, medical history, type of OAC and its dosage, concomitant medications, events related to stroke, systemic embolism, major bleeding, TIA, and myocardial infarction. | | | |

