9.3.3 Covariates

Logistic regression model was used to estimate propensity scores based on all covariates listed below:

- ✓ Age
- ✓ Gender
- ✓ Speciality of prescribers of OAC
- ✓ Time from AF diagnosis to initiation of OAC
- ✓ History of stroke or transient ischemic attack yes/no
- ✓ History of myocardial infarction yes/no
- ✓ History of coronary artery disease yes/no
- ✓ History of heart failure yes/no
- ✓ History of diabetes mellitus yes/no
- ✓ History of dyslipidemia yes/no
- ✓ History of arterial hypertension yes/no
- ✓ History of peripheral artery disease yes/no

- ✓ History of peptic ulcer disease yes/no
- ✓ History of dementia yes/no
- ✓ History of malignant lymphoma yes/no
- ✓ History of leukemia yes/no
- ✓ History of solid tumor cancer yes/no
- ✓ History of kidney impairment yes/no
- ✓ History of liver disease yes/no
- ✓ History of valvular disease yes/no
- ✓ History of bleeding (gastro-intestinal, etc.) yes/no
- ✓ History of hospitalization yes/no
- ✓ CHA₂DS₂-VASC
- ✓ HAS-BLED Score
- ✓ Year of Initiating Treatment
 - Index date falling within 12 months starting from 14th of March in 2011 and then from 1st of March of each respective year in 2012 to 2016, then to 30 June 2016.
- ✓ Concomitant medication (prescription claims within the baseline period)
 - yes/no for the following:
 - ◊ aspirin
 - ◊ ticlodipine
 - ◊ cilostazole
 - ◊ clopidogrel
 - ◊ angiotensin receptor blockers or angiotensin converting enzyme inhibitors
 - ◊ beta-blocker
 - ◊ amiodarone
 - ◊ procainamide
 - ◊ disopyramide
 - ◊ flecainamide
 - ◊ pilcicainide
 - ◊ procainamide
 - ◊ calcium-channel blocker
 - ◊ digoxin
 - ◊ diuretics
 - ◊ statins
 - ◊ proton-pump inhibitor
 - ◊ H₂ receptor antagonist

The disease, condition/disease for AF risk score calculation, AF risk score, and concomitant medication are defined as [Table 4](#), [Table 5](#), [Table 6](#), [Table 7](#), [Table 8](#).

Table 4

Definition of clinical history

| Disease | Definition | |
|-------------------------------------|---|---|
| | ICD10code | prescription |
| Stroke or transient ischemic attack | I60-I64, G45 | - |
| Myocardial infarction | I21-I23 | - |
| Coronary artery disease | I251 | - |
| Heart failure | I110, I130, I132, I420, I50 | Prescribed furosemide (defined by generic name) |
| Diabetes mellitus | E100, E101, E109, E110, E111, E119, E14 | Prescribed drugs used in diabetes (defined by ATC code as A10) |
| Dyslipidemia | E78 | - |

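### The DVT/PE exclusion looks back from AF diagnosis, not from anticoagulant start, so on a single-date reading it keeps thromboses recorded between the two dates

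*Combined protocol and SAP*

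**What the plan says.** Section 9.2, exclusion criterion 4, reads: "Having record of deep vein thrombosis or pulmonary embolism <6 months before AF diagnosis in baseline period". The abstract has the same rule with the same anchor: "having record of deep vein thrombosis or pulmonary embolism < 6 months before AF diagnosis in baseline period". Table 1 identifies the two conditions by ICD-10 codes I802 and I269.

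The other dates in section 9.2 hang on the prescription. The index date is given as "Index date: the date of first oral anticoagulant prescription, namely warfarin or dabigatran", and the lookback year as "Baseline period: 12 months prior to and including the index date". Inclusion criterion 1 requires a confirmed NVAF diagnosis (I48) but sets no limit on the time between that diagnosis and OAC start. Section 9.3.3 enters "Time from AF diagnosis to initiation of OAC" in the propensity model, so the plan expects the interval to vary.

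Section 9.11 states the aim of the criteria: to select patients with non-valvular AF who "have newly initiated oral anti-coagulants for stroke prevention".

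**The concern.** The criterion appears meant to keep out patients whose anticoagulant may have been started for venous thrombosis. For that purpose the date that matters is the first OAC prescription, yet the window counts back from AF diagnosis. The two dates can lie far apart. A patient with long-standing AF and a DVT one week before the first OAC prescription then passes every criterion, although the thrombosis is a plausible reason for the prescription.

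If such patients are distributed unequally between warfarin and dabigatran, the comparison carries some confounding that matching does not address directly. Follow-up is as-treated, so any difference in intended treatment duration would also affect person-time and censoring. Section 9.1 presents control of channelling bias as the strength of the design, so a gap in the rule on alternative indications deserves attention.

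**Working it through.** The plan gives no figure on this point to reproduce. The check is date logic, followed by an illustration of scale.

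**Date logic.** Measure time in months before the index date (index = 0). Let *a* be the AF diagnosis and *v* the DVT/PE record. The rule requires v ≥ a and v − a < 6, plus the baseline condition. That condition is grammatically open, so three readings were tested:

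- A: the DVT/PE record lies in baseline (v ≤ 12).
- B: the AF diagnosis lies in baseline (a ≤ 12).
- C: both do.

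| AF diagnosis (a) | DVT/PE (v) | Excluded under A / B / C | Inside a 6-month window before index |
|---|---|---|---|
| 36 | 0.25 | no / no / no | yes |
| 9 | 1 | no / no / no | yes |
| 3 | 1 | no / no / no | yes |
| 1 | 3 | yes / yes / yes | yes |
| 0 | 1 | yes / yes / yes | yes |
| 11 | 12.5 | no / yes / no | no |

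If a > 12, reading A needs v ≥ a > 12 and v ≤ 12 at once, which is impossible. Readings B and C fail on a ≤ 12. The rule then removes nobody on any reading.

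**How partial the miss is.** Take an even grid of DVT/PE dates from 0.1 to 5.9 months before index (59 points). The share that the rule catches is:

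- AF at index: 59/59 = 100%
- AF 1 month before: 50/59 = 85%
- AF 3 months before: 30/59 = 51%
- AF 6 or more months before: 0%

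The grid describes the rule. It does not estimate patient numbers.

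**Whether matching covers it.** I802 and I269 do not appear in the section 9.3.3 covariate list, in Table 4 (clinical history) or in Table 6 (risk-score conditions). Section 9.7.1 adds no covariates to the Cox model because no imbalance remained after matching. A balance check on the listed covariates says nothing direct about DVT/PE.

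**Scale, on assumed inputs.** The documents give no DVT/PE frequencies. Suppose 2% of warfarin and 0.5% of dabigatran patients have a missed DVT/PE (0.02 × 4,421 = 88 and 0.005 × 4,421 = 22) and twice the outcome rate.

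- Factor on the hazard ratio: (1 + 0.005)/(1 + 0.02) = 0.985, a log bias of −0.015.
- With the proportions swapped: 1.02/1.005 = 1.015. With equal proportions: 1.

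For precision, use the section 9.5 inputs: 4,421 per group, 0.40487 years, a rate of 0.03 per year (taken here as the warfarin rate) and HR 0.716.

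- Person-years per arm: 4,421 × 0.40487 = 1,790
- Events: 1,790 × 0.03 = 53.7 and 53.7 × 0.716 = 38.4
- SE(log HR) = √(1/53.7 + 1/38.4) = 0.211
- 95% CI factor: exp(1.96 × 0.211) = 1.51 each way
- Bias relative to SE: 0.015/0.211 = 7%

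For the bias to reach one standard error, with a doubled rate and 0.5% in the dabigatran arm, the warfarin proportion would have to be 1.005 × exp(0.211) − 1 = 24%.

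**The case against.** The strongest objection is that the AF date in criterion 4 is never defined. In claims data I48 recurs, and the wording could cover any I48 record in the baseline year, which includes the index date. A record at or near the first prescription would carry the 6-month window close to OAC start, and the gap would largely close even for long-standing AF. This stands as a limit on the point. The time-from-diagnosis covariate implies a single date, which makes that reading the more natural one, but it is not the eligibility rule. The text has to say which applies.

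Second, every enrolled patient has NVAF, and section 8 frames the objectives by AF and new treatment, not by indication. A reader might infer that the kept patients were anticoagulated because of their thrombosis. The documents record no indication and do not support that. They support only that such patients can enter, against the aim stated in section 9.11.

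Third, a reader might infer that any resulting imbalance is wholly uncontrolled. That goes too far: hospitalization history, solid tumour, prescriber specialty, time from AF diagnosis, bleeding history and HAS-BLED are in the model and may act as partial proxies.

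Fourth, the AF anchor may have been chosen deliberately. The documents give no such reason, but it argues for adding to the rule and not replacing it. With AF at 5 months and DVT at 9 months, the present rule excludes (9 − 5 = 4 < 6), while a 6-month window from index alone would admit.

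**Conclusion.** The point holds in a limited form. On the single-date reading, criterion 4 does not exclude a thrombosis recorded between AF diagnosis and OAC start, and it has no effect when AF was diagnosed more than 12 months before index. Both results hold on all three readings of the baseline condition. They would not hold if any repeat I48 claim counts as the AF diagnosis.

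It would be wrong to conclude that the exclusion fails in general, since it works fully when AF is diagnosed at index and mostly when AF is diagnosed shortly before. It would also be wrong to take 1.5% as the bias in this study. That figure rests on assumed proportions and an assumed doubling of the rate, and its sign reverses if the imbalance does. Size and direction are unknown. Against a standard error of about 0.21 the effect is probably small, and the plan declares its results exploratory. The reason to act is that the rule does not match its stated purpose and can be corrected with data already held.

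**What to change.** Keep the present exclusion and add a second limb: a DVT or PE record within 6 months before, or on, the index date. A simpler alternative is to exclude any DVT/PE record in the 12-month baseline period. This covers everything the present rule removes under readings A and C, but not the older events that reading B reaches (AF at 11 months, DVT/PE at 12.5). In either case, define the AF date used (first recorded I48 or any I48 claim), say which record the baseline condition qualifies, and use identical wording in the abstract and section 9.2.

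The cost is a small loss of eligible patients and a re-run of cohort selection, propensity matching and the balance check, because the matched size and the balance statement in sections 9.5 and 9.7.1 come from earlier work.

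If that earlier matched cohort must be kept, report DVT/PE before index by arm and repeat the primary and secondary comparisons without these patients as a sensitivity analysis.

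### Table 1 finds a mechanical valve only through T820 or a placement procedure in the 12-month baseline and lists no status code, so an uncomplicated older valve is missed by that row

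*Combined protocol and SAP*

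**What the plan says.** Exclusion criterion 3 in section 9.2 reads: "Having atrial flutter, valvular AF, mechanical valve placement, rheumatic AF, mitral valve prolapse/regurge/stenosis in baseline period". The window is set in the same section: "Baseline period: 12 months prior to and including the index date". The conditions "are defined by ICD-10 code, disease name, or medical care activity name (see Table 1"), so the three columns of Table 1 are alternative routes.

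The mechanical valve row uses two of the three:

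- ICD-10 code: "Mechanical valve placement | T820", and no other code.
- Disease name: empty.
- Medical care activity name: "Including “mechanical valve placement".

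The kidney transplant row of the same table lists two codes: "Kidney transplant | T861, Z940".

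Section 9.11 gives the purpose of the criteria, which is to "select those Japanese atrial fibrillation patients who have non-valvular etiology". Inclusion criterion 3 adds a separate filter: "No prescription of other OACs for 12 months prior to the index date, defined as the first prescription of OACs".

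**The concern.** A mechanical valve is a lasting state, but both routes in the row detect events. In ICD-10, the scheme the plan adopts, T820 is a mechanical complication of a heart valve prosthesis: the word describes the complication, not the type of valve. The procedure name picks up an implantation, and only one claimed at a contributing hospital within the 12 months up to index. A working valve implanted before that window, or elsewhere, triggers neither.

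The protocol does not print the meaning of these codes. What can be checked in the text is the asymmetry: the transplant row pairs a T code with a Z code, and the valve row has only the T code.

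At stake is the non-valvular definition of the cohort. Patients anticoagulated because of a mechanical valve would be expected mainly on warfarin. If their event rates are higher than those of the other warfarin patients, the warfarin rates rise and the hazard ratio (dabigatran over warfarin) falls.

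**Working it through.** **Step 1. Can a patient with an uncomplicated older valve get through?** The patient must pass every filter in section 9.2.

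| Filter | Does it stop the patient? |
|---|---|
| T820 in baseline | No, if there is no recorded complication |
| Placement procedure in baseline | No, if implanted earlier or at a non-contributing hospital |
| At least 12 months of enrolment | Only if the patient is new to the database |
| No oral anticoagulant in the prior 12 months | Yes, if any earlier prescription is visible |
| Other valve rows: I05-I09, I340-I342, disease name Valvular AF | Yes, if recorded in baseline. No row covers non-rheumatic aortic valve disease |

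The last two filters do the real work, and both depend on what is captured. Section 9.9 says that visits to non-DPC institutions are not in the data. Section 9.11 says that the database receives claims from approximately 12% of DPC hospitals. A patient seen at a contributing hospital for other care, with warfarin prescribed elsewhere, looks untreated until the first prescription at that hospital. The path exists, but it is narrow.

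**Step 2. Would matching repair it?** The valvular disease covariate (section 9.3.3, Table 4) lists I059, I089, I358, I38 and I48. None is a prosthesis code. I48 is also the inclusion code for atrial fibrillation, so as written the covariate is positive for essentially every included patient and separates nobody. The Cox model in section 9.7.1 adds no covariates. Neither step identifies these patients.

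**Step 3. How large could the effect be?** The plan states no figure for this point.

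Inputs from section 9.5 and Table 9: 4,421 per group, 0.40487 years of follow-up, a rate of 0.03 per patient-year (taken here as the warfarin rate) and a hazard ratio of 0.716 (read as dabigatran over warfarin, as in section 9.7.1). The hazard ratio reproduces: exp(0.21 × ln 0.45 + 0.79 × ln 0.81) = 0.716.

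- Warfarin events: 4,421 × 0.40487 × 0.03 = 53.7.
- Dabigatran events: 53.7 × 0.716 = 38.4.
- Standard error of the log hazard ratio: √(1/53.7 + 1/38.4) = 0.21.

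Let f be the share of matched warfarin patients with an undetected valve, and r their event rate relative to the other warfarin patients. If none are in the dabigatran arm, the observed hazard ratio is 0.716 / (1 + f(r − 1)), and the excess events are 53.7 × f(r − 1). The documents give neither f nor r; the values below are assumptions.

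| f | r | Patients (4,421 × f) | Excess events | Hazard ratio | Change |
|---|---|---|---|---|---|
| 0.5% | 2 | 22 | 0.3 | 0.712 | −0.5% |
| 1% | 2 | 44 | 0.5 | 0.709 | −1.0% |
| 2% | 3 | 88 | 2.1 | 0.688 | −3.8% |
| 3% | 4 | 133 | 4.8 | 0.657 | −8.3% |

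On the log scale the first two rows shift the estimate by ln 1.005 = 0.005 and ln 1.01 = 0.010, against a standard error of 0.21. The last row shifts it by ln 1.09 = 0.086, about 0.4 standard errors.

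**The case against.** The strongest reply is that the row does what the criterion says. Criterion 3 speaks of valve placement in the baseline period, and the procedure name is a full alternative route that captures it. A reader who sees only the ICD-10 cell might infer that the plan relies on T820 alone. It does not.

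A reader might also infer that patients with older mechanical valves pass freely into the warfarin arm. The documents do not support that either. Such a patient needs a year of enrolment, no visible anticoagulant in that year and no other listed valve code. Someone treated for the valve at the contributing hospital would normally be stopped by the anticoagulant rule.

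Third, the yield of a status code is unknown. Nothing in the documents shows how completely Z952 is recorded in this database, and under the present window it would help only if recorded within the 12 months.

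All three points stand, and they limit the size of the problem. They do not remove it. The anticoagulant rule tests visible prescribing, not valve status, and it fails in the situation that sections 9.9 and 9.11 describe. The third point is a reason to add a disease name and a longer search alongside the code.

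**Conclusion.** The mechanical valve row is incomplete for its stated purpose. It detects a complication or a recent operation, not the presence of a valve, and the transplant row shows that the plan used a status code where it wanted to capture a lasting condition. The gap is only partly covered by other filters, and matching cannot correct what gets through.

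The likely direction favours dabigatran. This assumes that affected patients are mainly on warfarin and have higher event rates than the other warfarin patients; the documents quantify neither. The same reasoning would apply to major bleeding, but there is no figure for it.

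A reader might infer a material bias in the hazard ratio. The documents do not support that. With f up to 1% and r = 2 the shift is 1% or less, and only the extreme corner reaches about 8%. The case for the change is that it is cheap and makes the exclusion match section 9.11, not that the result is known to be distorted.

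**What to change.** In the mechanical valve row of Table 1, add the prosthetic-valve status code (Z952, to be confirmed against the ICD-10 version in the database) and a prosthetic-valve disease name. Keep T820 and the procedure name. Any one route should suffice.

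For this condition, search all available history up to and including the index date, not only the 12-month baseline. Reword exclusion criterion 3 so that it covers the presence of a valve and not only its placement.

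Apply the rule before propensity matching, and report how many patients each route removes per arm. That count replaces the assumed f with evidence on how many were being missed.

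The cost is a revised table row and a rerun of cohort selection, matching and the balance check. A few patients with a bioprosthetic or unspecified valve may also be removed. If Z952 turns out to be rarely recorded, the disease name carries most of the work, and what remains undetected should be stated as a limitation in section 9.9.
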